Patients with cardiogenic shock, regardless of the underlying etiology, present with hypotension, shortness of breath, altered mental status, signs of volume overload (elevated jugular venous pressure, pulmonary rales, lower extremity edema), and evidence of end-organ hypoperfusion. These patients are typically admitted to the Coronary Care Unit (CCU) for aggressive treatment to reverse the course of the disease. Standard of care therapy for these patients involves initiation of ionotropes and/or vasopressors along with diuretics. Often, mechanical circulatory support (i.e. Intra-arterial balloon pump or temporary left-ventricular assist devices) and invasive hemodynamic monitoring (i.e. placement of a pulmonary artery catheter) is necessary.

The results of the small trials mentioned above are encouraging, but larger randomized trials are necessary to establish the role of TH in patients with cardiogenic shock. We propose a first-ever randomized clinical trial to prospectively study the effects of TH in patients with cardiogenic shock. In addition to assessing the safety of TH in this patient population, hemodynamic parameters, echocardiographic assessment of cardiac function during hypothermia, as well electrocardiographic changes with hypothermia will be studied. The echocardiographic changes during TH have never been previously reported. Studying TH in patients with cardiogenic shock is important, as therapies for this highly morbid condition have remained largely unchanged for many years. Given the high mortality associated with cardiogenic shock despite advances in medical and mechanical support, the clinical implications of results from this trial may be large.

Objective

The purpose of the study is to prospectively randomize patients with cardiogenic shock to standard therapy plus therapeutic hypothermia or standard medical therapy alone in order to assess the safety of TH in patients with cardiogenic shock. This study will also help understand the physiologic effects of TH in cardiogenic shock. This will be a pilot study to establish the safety of TH and to assess tolerability of TH in this patient population.

Methods

A. Patient Population:

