All patients meeting criteria for cardiogenic shock (defined as systolic blood pressure <90mmHg for at least 30 minutes, Cardiac Index < 2.2 L/min/m², pulmonary capillary wedge pressure (PCWP) ≥ 15mmHg, need for vasopressors, or need for mechanical support to keep systolic blood pressure ≥ 90mmHg) admitted to the University of Chicago Coronary Care Unit (CCU) will be randomized to standard medical therapy or to therapeutic hypothermia (32-34°) for 24 hours plus medical therapy in a non-blinded manner with 1:1 randomization using computer-generated random numbers (simple randomization). The cardiogenic shock may be a result of acute coronary syndromes (STEMI, NSTEMI, or UA), ischemic or non-ischemic cardiomyopathy, myocarditis, hypertrophic cardiomyopathy, stress-induced cardiomyopathy, peripartum cardiomyopathy, or cardiogenic shock in a patient with HF with preserved EF. Patients less than 18 years of age or greater than 89 years of age will be excluded. Patients with

baseline heart rate less than 60 beats per minute, baseline temperatures less than 35°C, recent cardiotomy, history of cardiac transplantation, or those who are pregnant will be excluded.

All patients between the ages of 18 and 89 who meet the criteria for cardiogenic shock in the CCU will be screened. Inclusion and exclusion criteria are listed below.

Inclusion Criteria:

- 1) Cardiogenic shock
 - a) Systolic blood pressure <90mmHg for at least 30 minutes
 - b) Cardiac Index < 2.2 L/min/m²
 - c) Pulmonary capillary wedge pressure (PCWP) ≥ 15mmHg
 - d) Need for central venous access, vasopressors, inotropes and/or mechanical circulatory support (i.e. intra-aortic balloon pump, Impella, ECMO) to maintain systolic blood pressure ≥ 90mmHg
- 2) Etiology of shock
 - a) Acute coronary syndromes (STEMI, NSTEMI, or UA)
 - b) Ischemic or non-ischemic cardiomyopathy
 - c) Myocarditis
 - d) Hypertrophic cardiomyopathy
 - e) Stress-induced cardiomyopathy
 - f) Peripartum cardiomyopathy
 - g) Cardiogenic shock in a patient with HF with preserved EF
- 3) Age ≥ 18 years AND ≤ 89 years
- 4) Admission to the University of Chicago CCU

Exclusion Criteria:

- 1) Baseline heart rate < 60 beats per minute
- 2) Baseline temperatures < 35°C
- 3) Recent cardiotomy
- 4) History of cardiac transplantation
- 5) Current pregnancy
- 6) Contraindication to 9.3 French femoral venous access for placement of intravascular cooling catheter

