5. TTE
6. Blood sample for future research

Endpoints

Primary safety endpoints:

1. Arrhythmia requiring medical therapy or therapy with temporary pacemaker
2. Bleeding requiring transfusions as a direct result of the cooling catheter insertion or secondary to resulting coagulopathy
3. Clinically important bloodstream infection, as confirmed with 2 positive blood cultures, or suspected sepsis in the absence of positive blood cultures with a sequential organ failure assessment (SOFA) score >2
4. Hypokalemia with potassium levels below 3.0mEq/L, not secondary to other identifiable causes

Secondary endpoints:

1. Hemodynamic changes during intervention period – Cardiac output/Cardiac Index, PCWP, SVR, mixed venous oxygen saturation (MVO₂), cardiac power index
2. Cumulative vasopressor and inotrope dose requirements (i.e. number of vasoactive and/or inotropic drugs used)
3. Echocardiographic % change in ejection fraction at 18-24 hours (from baseline)
4. In-hospital all-cause mortality

Procedures

Patients admitted to the Coronary Care unit (CCU) at the University of Chicago will be screened by the study investigators and the cardiology fellow on the CCU rotation. Patients meeting the inclusion criteria, as defined previously, will be identified and randomized after informed consent within 12 hours of presentation. Patients will be randomized to either TH plus standard medical care or to standard medical care alone. A pulmonary artery (PA) catheter will be placed at the bedside or in the Cardiac Cath lab if difficult anatomy is anticipated. As mentioned earlier, placement of a PA catheter is part of the standard of care for management of cardiogenic shock. Currently, patients who are admitted to the University of Chicago CCU with cardiogenic shock routinely undergo placement of PA catheter by the cardiology fellow in the CCU or in the cardiac cath lab. Data from the PA catheter is vital in initiating vasopressors/inotropes, assessing the response to the therapies, and possible need for escalation of therapy (i.e. mechanical support). In this study, patients in each arm will undergo PA catheter placement.

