administration of medications or a dialysis catheter for temporary dialysis. After successful insertion of the cooling catheter, it will be connected to the Thermogard XP® thermal regulation system. The Quattro® catheter functions as both a central venous triple lumen catheter as well as a cooling catheter. Cooling is achieved by circulating normal saline in a closed system through the catheter. The flow and temperature (range 4°C to 42°C) of the circulating saline serves as the heat exchange mechanism and is controlled by the external Thermoguard® thermal regulation system. The temperature is measured and adjustments are made by the thermal regulation system to automatically maintain target temperature. The target temperature is achieved within 2-3 hours of initiation of TH. Rewarming is accomplished using the same balloon catheter system and heat exchange occurs without infusion of any saline or fluids into the patient. In clinical trials, intravenous catheter based cooling system has been shown to achieve target temperature faster and maintain target temperature with more precision.^{12,14,15}

Medical therapy in both intervention and non-intervention groups will be based on the current recommendations for management of cardiogenic shock. This includes inotropic therapy (i.e. dobutamine or milrinone) for cardiac support, vasopressor therapy (i.e. norepinephrine, dopamine, phenylephrine, epinephrine) to achieve target blood pressure (mean arterial blood pressure \geq 60 mmHg), diuretics for volume removal, and mechanical circulatory support as clinically indicated. All patients included in this study will have pulmonary artery (PA) catheters inserted within 12 hours of randomization via either the internal jugular or femoral venous approach to monitor real-time hemodynamics. The clinicians in the CCU will use the data from PA catheters (cardiac output, mixed venous saturation, systemic vascular resistance, etc.) to guide therapy for both the intervention and non-intervention groups. The primary investigator of this study ([name]) will have no role in the clinical management of the patients.

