Laboratory, echocardiographic, and hemodynamic parameters will be obtained for patients prior to randomization, near the end of 24 hour cooling therapy, and after 48-96 hours post-randomization. Core temperature will be measured via either thermal tip at the end of a transurethral urinary catheter or endotracheal temperature probe in intubated patients. Rewarming will be accomplished at 0.3°C per hour until temperature reaches 37°C.

Target Enrollment and Study Duration

In this initial pilot study, we anticipate enrolling 20 patients to the study, 10 randomized to standard medical therapy and 10 patients randomized to standard medical therapy and 24 hours of TH. We anticipate completing enrollment within 6 months.

Statistical Methods

The three-dichotomous primary endpoints will be analyzed using a two-sample independent proportion test or a Fisher's exact test with a Bonferroni method continuity correction for multiple endpoints. Furthermore, numerical secondary endpoints will be presented as either

mean \pm standard deviation or median (interquartile range) based upon the distribution of the data. In addition, all numerical secondary endpoints will be assessed using two independent t tests or Mann-Whitney U test for comparisons. Categorical variables will be tested with chi-square tests of association or Fisher's exact tests. Differences will be considered significant using an alpha value of 0.05 for a two-sided test. Analyses will be performed using STATA MP Version 14 (College Station, TX).

Potential risks and benefits to subjects

A. Benefits:

There is mounting evidence that TH has positive effects on cardiac function. Multiple studies have suggested that TH may offer particular benefit in cardiogenic shock. In this prospective trial, the patients will be randomized to TH or standard medical care using simple randomization. With TH, we expect increased cardiac output, increased contractility, lower SVR, and higher cardiac power index which will lead to improved hemodynamics and potentially decreasing pressor requirements.

B. Risks:

Anticipated adverse events that could possibly occur during the study include, but are not limited to:

1. *Risks associated with TH*
 - a. Shivering
 - b. Arrhythmia
 - c. Coagulopathy with or without clinically significant bleeding
 - d. Hyperglycemia
 - e. Hypothermia
 - f. Electrolyte abnormalities
 - g. Infections
2. *Risks associated with cooling catheter insertion*
 - a. Bleeding
 - b. Infection

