The risks associated with insertion of a cooling catheter are the same as insertion of any central lumen catheter. These include, but are not limited to, bleeding, infection, and vascular injury. Previously published studies have quoted risk of localized hematomas at 4.7% and risk of vascular injury (most frequently due to inadvertent arterial puncture) at $<1\%$.²³ Incidence of line-associated blood stream infection has been reported as 80-189 episodes per 100,000 patient years.²³

Insertion of a central venous catheter is standard of care in patients in cardiogenic shock to allow for administration of inotropes/vasopressors. The ZOLL Quattro catheters include three standard

central venous catheter infusion lumens to allow for administration of these vasoactive medications. Therefore, patients randomized to TH arm will not need an additional central venous line. Rather, insertion of a cooling catheter will serve the purpose of initiation and maintenance of TH while also allowing for administration of drugs via the infusion lumens. The risk associated with cooling catheter insertion is not expected to be higher than insertion of a standard central venous line.

C. Monitoring of Safety:

During the intervention period, participants will be monitored by physicians, nurses, and technicians in accordance with standard medical care. This includes 24-hour monitored telemetry, with measurement of heart rate, blood pressure, oxygen saturation, and respiratory rate. Real-time hemodynamic monitoring will be measured using pulmonary artery catheters. Blood glucose and electrolyte measurements will be performed as per protocol for patients undergoing therapeutic hypothermia, and correction of abnormalities will be performed by the treating team. Shivering will be monitored by the treating nurse, per ICU protocol, and will be reported to the treating team. TH will not influence the clinician's medical decisions – any medical or mechanical intervention necessary based on clinical status will be allowed.

D. Data Safety Monitoring Board:

Adverse events will be reviewed by the Data Safety Monitoring Board as described below. The study will be halted upon the discovery of unanticipated adverse device events that present a significant or unreasonable risk to subjects enrolled in the study.

The DSMB will meet (in person or via telephone conference) a minimum of 3 times:

- after treatment of the first 4 subjects (2 in the TH arm and 2 in the control arm)

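### Primary safety endpoint 2 counts only transfused bleeding caused by cooling, so the control count is expected to be zero by construction and the planned between-arm test cannot compare bleeding.

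*Combined protocol and SAP*

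**What the plan says.** Endpoints lists four primary safety endpoints. The second is "Bleeding requiring transfusions as a direct result of the cooling catheter insertion or secondary to resulting coagulopathy". Statistical Methods states that "The three-dichotomous primary endpoints will be analyzed using a two-sample independent proportion test" or by Fisher's exact test, with a Bonferroni adjustment and a two-sided alpha of 0.05. It does not say which of the four listed endpoints make up the three.

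The Objective is to randomize against "standard medical therapy alone in order to assess the safety of TH in patients with cardiogenic shock" (TH is therapeutic hypothermia). Target Enrollment is 20 patients, 10 per arm. Allocation is by simple randomization and is not blinded (Patient Population).

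Controls have bleeding sources of their own:

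- Procedures: "In this study, patients in each arm will undergo PA catheter placement".
- Procedures also allows both arms "mechanical circulatory support as clinically indicated".
- Mitigating Risks associated with cooling catheter insertion: "Insertion of a central venous catheter is standard of care in patients in cardiogenic shock".

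**The concern.** A randomized control arm in a safety study supplies the background event rate. Endpoint 2 closes off that rate by definition, because a control bleed from a pulmonary artery catheter, a central line or a support device cannot qualify. An arm difference in endpoint 2 therefore cannot be read as a difference in bleeding, and a lower bleeding rate under hypothermia could never appear. The plan expects the cooling catheter to carry no more risk than a standard central line, but this endpoint cannot examine that, because standard-line bleeds in controls never count. Whether a bleed in the hypothermia arm counts depends on a causal judgement made with the arm known.

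Endpoint 4 (potassium below 3.0 mEq/L without another identifiable cause) has a milder form of the problem. It is worded neutrally between arms, but the risk section names diuretics as one such cause, and diuretics are part of therapy in both arms. Appendix 1 schedules 4-hourly potassium for cooled patients only.

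**Working it through.** The plan states no event rate, power or derived sample size for this endpoint, so there is no figure of its own to reproduce.

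**1. Who can count.** A bleed qualifies only through the cooling catheter or the coagulopathy that results, and the risk section presents coagulopathy as a risk of hypothermia. Controls have standard care alone. The one route to a control event is a control who is cooled clinically, since Monitoring of Safety says "any medical or mechanical intervention necessary based on clinical status will be allowed". Hence the control count is expected to be zero, not certain to be.

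**2. Inputs.** From the documents: 10 per arm; alpha 0.05 two-sided; Bonferroni 0.05/4 = 0.0125 (four endpoints) or 0.05/3 = 0.0167 (three). Assumed: true transfused-bleed rate r, equal in both arms, of 10%, 20% or 30%; share s of hypothermia-arm bleeds attributed to cooling of 0, 0.5 or 1.

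**3. Control bleeds left out and expected difference.** Expected number left out = 10r. Chance of at least one = 1 − (1 − r)^10. Expected difference as written = r × s − 0; the true difference is r − r = 0.

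| r | Control bleeds left out | P(at least one) | s = 0 | s = 0.5 | s = 1 |
|---|---|---|---|---|---|
| 10% | 1 | 65% | 0 | +5 points | +10 points |
| 20% | 2 | 89% | 0 | +10 points | +20 points |
| 30% | 3 | 97% | 0 | +15 points | +30 points |

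The sign can reverse. With 20% under hypothermia, 40% in controls and s = 1, the true difference is −20 points and the endpoint shows +20.

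**4. The planned tests against 0/10.** Fisher's two-sided p is 0.0325 for 5/10 and 0.0108 for 6/10, so 6/10 is the threshold at both 0.0167 and 0.0125. False rejection is P(X ≥ 6), with X binomial (10, r × s):

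- r = 20%: 0.6% if s = 1; 0.01% if s = 0.5.
- r = 30%: 4.7% if s = 1; 0.1% if s = 0.5.

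The plan also permits a two-proportion test. Without continuity correction, 5/10 v 0/10 gives z = 0.5/√(0.25 × 0.75 × 0.2) = 2.58, p = 0.0098, so 5/10 suffices. P(X ≥ 5) with s = 1 is 3.3% at 20% and 15.0% at 30%.

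**5. Unequal arms.** Simple randomization of 20 gives exactly 10/10 with probability 17.6%. Averaged over all splits with s = 1, Fisher's test falsely rejects 1.0% and 5.1% of the time at 0.0125, and 1.8% and 8.1% at 0.0167, for r = 20% and 30%.

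**6. Any-cause definition.** With equal rates of 20% and 30% at 10 v 10, Fisher's test rejects 0.1% and 0.3% of the time at either level. At 0.0125 its power is 5.9% for 20% v 50% and 12.9% for 20% v 60%. An observed 2/10 v 2/10 has a Newcombe 95% interval of −34 to +34 points.

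**The case against.** **It is a pilot.** It has 20 patients and no powered hypothesis, and a count of device-attributed bleeds is a reasonable pilot measure. That stands for description. It does not rescue the planned between-arm test, and the fault is one of meaning, not precision.

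**Control bleeds are recorded elsewhere.** Bleeding adverse events are graded by GUSTO, Table A of the DSMB charter defines adverse events without regard to arm or relatedness, and the DSMB makes the final adjudication. All true, and the DSMB's role is a real check on attribution, although the documents do not say it is blinded. None of this brings a control bleed into endpoint 2 or its test.

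**The rates are unsupported.** The plan's only bleeding-related figures are 4.7% for localized hematoma and under 1% for vascular injury, and neither is a transfused bleed. The sizes above are illustrations over a range. The structural point does not depend on them.

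**Dropping the test would be enough.** Reporting endpoint 2 descriptively would remove the invalid test. It would also leave a randomized safety trial with no bleeding comparison among its primary endpoints.

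**Endpoint 4 is a weaker case.** Agreed. Both arms also have a basic metabolic panel at all three in-hospital time points, and because potassium is repleted, the bias from unequal sampling could run either way.

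**Conclusion.** The concern holds. Endpoint 2 cannot compare bleeding between arms as defined, and it should be corrected because it is a primary endpoint of a trial randomized to assess safety. At assumed equal rates of 10% to 30%, the expected spurious difference runs from 0 to +30 points, according to the share of bleeds attributed to cooling. False significance is secondary: with Fisher's test and Bonferroni at 10 v 10 and rates of 20% and 30%, it is at most 4.7%. It is larger with uneven arms or the uncorrected proportion test. The conclusion rests on the plain reading that the coagulopathy in question is the one caused by cooling, and on endpoint 2 being among those tested, which the mismatch between three and four leaves open. Endpoint 4 is a lesser issue of the same kind.

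**What to change.** - **Endpoint 2:** count any bleeding requiring transfusion, from any cause, in both arms, graded by GUSTO, which the plan already names.
- **Window:** use one window anchored at randomization, for example to 96 h, the end of the last in-hospital column of Appendix 1. On the protocol's own times, cooling and rewarming end by about 12 + 3 + 24 + (37 − 32)/0.3 = 55.7 h, if cooling starts once the pulmonary artery catheter is in; no latest start is stated. Timing of Data Collection anchors the 48–96 h assessment at completion of cooling, whereas Procedures and Appendix 1 anchor it at randomization; these must be reconciled. The index hospitalization, over which adverse events are collected, is an alternative that would also catch later bleeds.
- **Attribution:** report relation to the cooling catheter or coagulopathy as a supportive descriptive analysis, using the Table B criteria.
- **Statistical Methods:** state that all four primary endpoints are tested, at 0.05/4 = 0.0125, and report each risk difference with a 95% interval. If three are intended, name them and use 0.05/3.
- **Adverse events:** align the treatment-emergent definition in the DSMB section, which is tied to use of hypothermia, with the arm-neutral definition in Table A.
- **Endpoint 4 (lower priority):** count any potassium below 3.0 mEq/L in both arms, report cause as supportive, and state that the arm difference is read in light of unequal sampling.

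The cost is the wording of two endpoints, one statistical sentence and one definition. Transfusion is not named in the data list, which is not exhaustive, so a record-review field may be needed for about 20 patients. No new visits, blood draws or procedures follow. Any-cause counts will include background bleeds, which the control arm is there to measure, and estimates will remain wide at this size.

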Appendix 2 – DSMB Charter

1. Introduction

This Charter is for the Data and Safety Monitoring Board (DSMB) for Cardiogenic Shock Intravascular Cooling Trial (CHILL-SHOCK). The DSMB will consist of a team of clinical researchers who are unaffiliated with this project. The members of the DSMB will not be investigators in this study and will be experienced in conducting and interpreting clinical trials. Their responsibilities will include reviewing the efficacy and safety endpoints at the set times points, as stated below. The Charter is intended to be a living document. The DSMB may wish to review it at regular intervals to determine whether any changes in the procedure are necessary.

2. Responsibilities of the DSMB

The DSMB is responsible for safeguarding the interests of study participants, assessing the safety and efficacy of study procedures, and for monitoring the overall conduct of the study.

The DSMB is an independent group advisory to the study PI and is required to provide recommendations about starting, continuing, and stopping the study. In addition, the DSMB is asked to make recommendations, as appropriate, to/about:

- Selection, recruitment, and retention of participants
- Adherence to protocol requirements
- Completeness, quality, and analysis of measurements
- Amendments to the study protocol and consent forms
- Confirmation of the PI's assessment of adverse events
- Final adjudication of all adverse events, as defined by *Table A* below
- Participant safety
- Notification of and referral for abnormal findings

3. DSMB Members

DSMB Chair: [name] University of Chicago Medicine Department of Medicine Section of Cardiology Assistant Professor of Medicine	[name], MSc Inova Health System Department of Medicine Section of Cardiology Professor of Medicine	[name] University of Chicago Medicine Department of Medicine Section of Cardiology Assistant Professor of Medicine
---------------------------------------------------------------------------------------------------------------------------------------------------------------------------	-----------------------------------------------------------------------------------------------------------------------------------------------	---------------------------------------------------------------------------------------------------------------------------------------------------

4. Scheduling, Timing, and Organization of Meetings: Data and Safety Monitoring Meetings

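### Primary safety endpoint 3, read literally, does not count suspected sepsis with SOFA >2 and exactly one positive blood culture, although it counts the same patient with none or with two

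*Combined protocol and SAP*

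**What the plan says.** In the combined protocol and SAP, under Endpoints, the third primary safety endpoint is a single sentence with two alternative limbs. The first is "Clinically important bloodstream infection, as confirmed with 2 positive blood cultures". The second follows directly: "or suspected sepsis in the absence of positive blood cultures with a sequential organ failure assessment (SOFA) score >2".

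Statistical Methods treats the primary endpoints as yes/no outcomes: "The three-dichotomous primary endpoints will be analyzed using a two-sample independent proportion test". Fisher's exact test is the alternative, with a Bonferroni adjustment for multiple endpoints. The level is given as follows: "Differences will be considered significant using an alpha value of 0.05 for a two-sided test". There is no indeterminate category. Target Enrollment and Study Duration sets the size, the 24 hours being the cooling period: "we anticipate enrolling 20 patients to the study, 10 randomized to standard medical therapy and 10 patients randomized to standard medical therapy and 24 hours".

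Elsewhere infection appears only as a risk, in the section on potential risks and benefits, with no culture rule attached. Section 2 of the DSMB Charter (Appendix 2) gives the board this task: "Final adjudication of all adverse events, as defined by" Table A. That table holds general device-safety definitions and no infection criterion.

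**The concern.** The two limbs do not meet. One needs two positive cultures and the other, on its face, allows none, so a patient with exactly one fits neither. Because the endpoint is dichotomous, failing both limbs means being scored as having no event.

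The resulting pattern is hard to defend. A patient who would count on clinical picture and SOFA score alone stops counting when one culture turns positive, and counts again when a second does.

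The endpoint matters because the Objective states: "This will be a pilot study to establish the safety of TH and to assess tolerability of TH in this patient population". Infection is also a listed risk of both the cooling and the catheter insertion, so this endpoint targets an anticipated harm. The level of the SOFA cut-off is a separate question and is not at issue here.

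**Working it through.** The plan states no figure on this point, so there is none to reproduce. The check is a truth table, followed by arithmetic on how much one patient weighs.

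**Step 1: the rule.** Let c be the number of positive blood cultures in a patient with suspected sepsis. The SOFA condition is taken to belong to limb 2 only. Where c is 2 or more, the infection is taken to have been judged clinically important.

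- Limb 1 is met if c ≥ 2.
- Limb 2, read literally, is met if c = 0 and SOFA > 2.
- Event = limb 1 or limb 2.
- For comparison, limb 2 read loosely is met if c < 2 and SOFA > 2.

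| Positive cultures | SOFA | Limb 1 | Limb 2, literal | Event, literal | Event, loose |
|---|---|---|---|---|---|
| 0 | ≤2 | no | no | no | no |
| 0 | >2 | no | yes | **yes** | yes |
| 1 | ≤2 | no | no | no | no |
| 1 | >2 | no | no | **no** | **yes** |
| 2 or more | ≤2 | yes | no | yes | yes |
| 2 or more | >2 | yes | no | **yes** | yes |

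At SOFA > 2 the literal result is yes, no, yes for 0, 1 and 2 positive cultures. The two readings differ in one cell only: one positive culture with SOFA > 2.

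**Step 2: does other text assign that cell?** The risk lists name infection without a culture rule. Statistical Methods offers only event or no event. The definitions in Table A are generic. None of them says how a single positive culture is classified for endpoint 3.

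**Step 3: weight of one patient.** With 10 per arm, 1/10 = 10 percentage points of that arm's event rate.

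**Step 4: a hypothetical test result.** The counts below are assumptions chosen for illustration. With 10 per arm and no control events, the two-sided Fisher p-value for x events in the hypothermia arm is 2 × C(10,x) / C(20,x).

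- x = 6: 2 × 210 / 38,760 = 0.0108
- x = 5: 2 × 252 / 15,504 = 0.0325
- x = 4: 2 × 210 / 4,845 = 0.0867

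Statistical Methods speaks of three primary endpoints and the Endpoints section lists four, so the Bonferroni level is either 0.05/3 = 0.0167 or 0.05/4 = 0.0125. That inconsistency is separate and does not alter this check. Moving from 6 v 0 to 5 v 0 takes p from 0.011 to 0.033 and crosses either level. Moving from 5 v 0 to 4 v 0 crosses only an unadjusted 0.05, so it changes no conclusion under the planned correction.

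**The case against.** The strongest reply is that a sensible reader would not apply the sentence literally. The second limb follows straight after the first, so its reference to positive cultures can be taken to mean the two confirmatory cultures just named. The endpoint would then be confirmed infection, or suspected infection without confirmation, and the one-culture patient would count. This reading is natural, so the literal outcome cannot be treated as settled. But the protocol does not adopt it. The trial is non-blinded (Methods, A. Patient Population), and under Data Safety Monitoring Board the principal investigator supplies the analysis of causality, severity and frequency that the board reviews. The choice of reading could therefore be made after the fact, by people who know the arm.

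A reader might infer that the plan loses real sepsis cases. The documents do not support that. The adverse event definition in Table A is broad, the serious category covers life-threatening deterioration, and events are collected through the index hospitalization with final adjudication by the board. A septic patient with one positive culture should stay in the safety record. This limits the harm, but an adverse event listing does not put the patient into the primary comparison.

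A third reply is that a single positive culture may be a contaminant, so it is not always further evidence of infection. That is fair, and it is a plausible reason to require two cultures in limb 1. It does not explain why one positive culture should cancel an event that limb 2 would otherwise count.

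Finally, 6 v 0 means infection events in 60% of the hypothermia arm and none in control, and no rate in the documents supports that. The only infection figure, under the risks of catheter insertion, is 80–189 line-associated infections per 100,000 patient-years. It points to rare events, although it does not cover all sepsis. The objection stands, and the example serves only as an illustration.

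**Conclusion.** The gap is real on the literal text, and no other section closes it. It concerns one cell of one primary safety endpoint: suspected sepsis, SOFA above 2 and exactly one positive culture. What the documents establish is ambiguity in the classification of that patient, with a perverse result on one of two available readings.

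The secure measure of size is 10 percentage points of an arm's rate per affected patient, assuming the planned 10 per arm. The expected number of affected patients cannot be computed and may be zero.

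A reader might go further and infer that the definition favours hypothermia or makes the safety comparison unreliable. The documents do not support this. The gap applies equally to both arms, no direction of bias can be shown, and the change of significance depends on an extreme hypothetical table.

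For a 20-patient pilot with no stated power or decision margin, this is a should-fix matter of wording.

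**What to change.** In primary safety endpoint 3, replace the condition in the second limb that no blood culture be positive with *not meeting the two-culture criterion*. Patients with no or one positive culture can then qualify through suspected sepsis and the SOFA score. Only the one-culture, SOFA > 2 cell changes. List one-culture cases with the organism in the safety table, so that readers can judge possible contaminants. It would also help to state whether two positive cultures means separate sets or the same organism.

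Make the change before any patient is classified on this endpoint. It costs one phrase and one line in a table. Sample size, procedures and clinical management are unaffected. The event count may rise slightly, and an occasional contaminant will be included in a patient who already meets the suspected-sepsis and SOFA criteria.
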